8.1.5 Supplemental Analysis

As another sensitivity analysis, the Cochran-Mantel-Haenszel (CMH) test stratified by the randomization stratification factors will be applied to the primary endpoint, and treatment comparisons between individual OPS-2071 dose groups vs. placebo will be conducted.

8.1.6 Subgroup Analysis

Subgroup analysis of the percentage of subjects who achieve clinical remission at week 12 will be conducted by gender, race (Caucasian and Non-Caucasian), age (18 to < 40, 40 to < 50, and at least 50), and region (US and non-US) using logistic regression with terms of treatment group, the randomization stratification factors, location of disease, disease duration, smoking habit, and baseline CDAI, and baseline CDAI with CDAI stratification factor interaction.

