3.3 Trial Population

Approximately 240 male and female subjects between the ages of 18 and 70 (inclusive), with Crohn's disease and showing symptoms of active inflammation despite ongoing

treatment, will be randomized. Active mucosal inflammation will be confirmed by centrally read ileocolonoscopy. Discontinued or withdrawn subjects will not be replaced.

4 Sample Size

For the primary endpoint of clinical remission (CDAI score < 150), assuming a 40% response rate in the OPS-2071 600 mg BID and 300 mg BID dose groups and a 20% response rate in the placebo group, 60 randomized subjects per treatment group would provide 80% power to detect a treatment difference between the OPS-2071 pooled dose groups (600 mg BID and 300 mg BID) and the placebo group in the primary endpoint, using a 2-sided alpha of 0.05. The total sample size of the trial is 240 randomized subjects with 1:1:1:1 randomization to OPS-2071 600 mg BID, 300 mg BID, or 150 mg BID, or placebo BID. The power of individual dose comparison with placebo under the same assumption is 67%.

For the secondary endpoint of endoscopic response, assuming a 26.5% response rate in the OPS-2071 600 mg BID and 300 mg BID dose groups and a 10% response rate in the placebo group, 60 subjects per treatment group would provide 80% power for the comparison between the OPS-2071 pooled dose groups (600 mg BID and 300 mg BID) and the placebo group, and 65% power for the individual dose comparison with placebo, using a 2-sided alpha of 0.05.

5 Statistical Analysis Datasets

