Appendix 4 List of Summary Tables

CT-1.1 Subject Disposition

CT-1.2 Subject Disposition by Country and Center

CT-1.3 Subject Completion Rates

CT-2 Reasons For Discontinuation

CT-3.1 Demographic Characteristics: Age, Weight, Height, BMI, Sex, Race, and Ethnicity

CT-3.2 Medical History

CT-4.1 Concomitant Medications: Medication Taken Prior to Start of Trial Therapy

CT-4.2 Concomitant Medications: Medication Taken During Trial Therapy

CT-4.3 Concomitant Medications: Medication Taken Post Trial Therapy

CT-5.1 Summary of the Percentage of Subjects Who Achieve Clinical Remission at Week 12

CT-5.2 Sensitivity Analysis of the Percentage of Subjects Who Achieve Clinical Remission at Week 12 Using Placebo-based Pattern Imputation

CT-5.3 Supplemental Analysis of the Percentage of Subjects Who Achieve Clinical Remission at Week 12 Using Cochran-Mantel-Haenszel (CMH) Test

CT-5.4 Subgroup Analysis of the Percentage of Subjects Who Achieve Clinical Remission at Week 12

CT-6.1 Summary of the Percentage of Subjects with Endoscopic Response at Week 12

CT-6.2 Summary of Change from Baseline in the SES-CD Score

CT-6.3.1 Summary of the Percentage of Subjects with PRO-2 Remission at Week 12

CT-6.3.2 Sensitivity Analysis of the Percentage of Subjects with PRO-2 Remission at Week 12 Using Placebo-based Pattern Imputation

CT-6.4 Summary of the Percentage of Subjects with Clinical Response at Week 12

CT-6.5 Summary of the Percentage of Subjects Who Achieve Endoscopic Remission at Week 12

CT-6.6 Summary of the Percentage of Subjects with a Decrease from Baseline of ≥ 100 Points in the CDAI Score

CT-7 Extent of Exposure to Trial Medication

CT-8.1 Adverse Events(All Causalities)

CT-8.2.1 Incidence of Treatment-Emergent Adverse Events by System Organ Class and MedDRA Preferred Term

CT-8.2.2 Incidence of Treatment-Emergent Adverse Events by System Organ Class, MedDRA Preferred Term and Severity

CT-8.3.1 Incidence of Potentially Drug-Related Treatment-Emergent Adverse Events by System Organ Class and MedDRA Preferred Term

CT-8.3.2 Incidence of Potentially Drug-Related Treatment-Emergent Adverse Events by System Organ Class, MedDRA Preferred Term and Severity

CT-8.4. Incidence of Deaths due to Treatment-Emergent Adverse Events by System Organ Class and MedDRA Preferred Term

CT-8.5.1 Incidence of Serious Treatment-Emergent Adverse Events by System Organ Class and MedDRA Preferred Term

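### Subgroup analyses (SAP 8.1.6) in effect fit a logistic model of about 13–14 parameters inside each level, with no treatment-by-subgroup test and no rule for small levels

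*SAP*

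**What the plan says.** SAP 8.1.6 analyses the proportion in clinical remission at Week 12 by gender, "race (Caucasian and Non-Caucasian), age (18 to < 40, 40 to < 50, and at least 50), and region (US and non-US". That makes 2 + 2 + 3 + 2 = 9 levels. The method is stated as "using logistic regression with terms of treatment group, the randomization stratification factors, location of disease, disease duration, smoking habit, and baseline CDAI", together with "baseline CDAI with CDAI stratification factor interaction".

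The primary model in SAP 8.1.2 also contains country, age and sex. The subgroup model drops these three, and race was in neither. The only interaction listed is between baseline CDAI and its own stratum.

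Appendix 4 adds a table title, "CT-5.4 Subgroup Analysis of the Percentage of Subjects Who Achieve Clinical Remission at Week 12", and nothing about its content. Neither document gives an expected size for any level, a minimum size for analysis, a rule for non-convergence or sparse data, or the coding of disease location and smoking habit.

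SAP section 11 states that the planned analyses will not be performed, because the trial stopped with three randomized subjects.

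**The concern.** Removing sex, age and country from the covariates makes sense if the model is run inside each level of those factors, and makes little sense in a single model meant to compare levels. The SAP does not use the word separately, but fitting by level is the natural reading. Two things follow.

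First, a model built for 240 subjects is carried almost whole into levels that may hold a small fraction of them. With few remissions, some combination of covariates can split remitters from non-remitters perfectly or nearly so (separation). Maximum likelihood then gives infinite coefficients, and the reported odds ratio and Wald interval mean nothing.

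Second, level-by-level fits give one treatment estimate per level but no test of whether those estimates differ. With low power in each level, a significant result in one level beside a non-significant one in another is likely even when the true effect is the same in both.

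**Working it through.** **The plan's own figure.** SAP section 4 states "60 randomized subjects per treatment group would provide 80% power" for 600 and 300 mg pooled against placebo, and 67% for a single dose, at 40% versus 20% remission and 2-sided alpha 0.05. Normal approximation with pooled variance under the null, power = Φ[(d − 1.96·SE0)/SE1]:

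- Pooled, 120 v 60: mean rate (60×0.2 + 120×0.4)/180 = 0.333; SE0 = √(0.333×0.667×(1/60 + 1/120)) = 0.0745; SE1 = √(0.16/60 + 0.24/120) = 0.0683; (0.2 − 1.96×0.0745)/0.0683 = 0.79; power 78.5%, against 80% stated.
- Single dose, 60 v 60: SE0 = √(0.21×2/60) = 0.0837; SE1 = √(0.40/60) = 0.0816; power 67.0%, as stated.

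The planning rates therefore reproduce to within 2 points. The SAP gives no figure for subgroups.

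**Parameter count.** Intercept 1 + treatment 3 + CDAI stratum 1 + medication stratum 2 + location 2 (ileum, colon, both: assumed) + duration 1 + smoking 1 or 2 (two or three categories: assumed) + baseline CDAI 1 + interaction 1 = 13 or 14. Pooling the two high doses would give 12 or 13.

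**Separation check.** Remission was set at 20% on placebo and 40% on 300 and 600 mg (SAP section 4). The documents give no rate for 150 mg, so 20% and 30% were both used. Further assumptions: equal arms, medication strata 40/20/40%, 65% in the lower CDAI stratum, three equal locations, smoking 75/25% or 55/25/20%. There were 300 data sets per setting. With s = +1 for remission and −1 otherwise, separation is present when the maximum of Σ s·x′β, subject to every s·x′β ≥ 0 and |β| ≤ 1, exceeds zero. Simulation standard error is at most √(0.25/300) = 2.9 points.

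Expected remissions use the average rate: (20+20+40+40)/4 = 30%, or 32.5% with 150 mg at 30%.

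| Level size | Share of 240 | Expected remissions | No finite solution | Treatment coefficient not finite |
|---|---|---|---|---|
| 24 | 10% | 7–8 | about 90–97% | 83–93% |
| 36 | 15% | 11–12 | 40–59% | 32–44% |
| 48 | 20% | 14–16 | 16–34% | 10–19% |
| 60 | 25% | 18–20 | 7–16% | 3–6% |
| 72 | 30% | 22–23 | 5–9% | 3–5% |
| 100 | 42% | 30–33 | 1% or less | under 1% |
| 120 | 50% | 36–39 | under 1% | under 1% |

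The fourth column combines this run with a repeat that came out somewhat lower (89–94% at 24, 40–56% at 36, 7–16% at 60). The last column is from the first run.

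**Power inside a level.** The same formula for the pooled 20-point effect, unadjusted, gives 47% at 120 subjects, 25% at 60 and 11% at 24.

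**Power of an interaction test.** Pooled high doses against placebo, 180 subjects, a fraction f in the level with no effect and the rest with a 20-point effect:

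variance = 0.16/(60f) + 0.16/(120f) + 0.16/(60(1−f)) + 0.24/(120(1−f)); power = Φ(0.2/√variance − 1.96).

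- f = 0.5: variance 0.0173, 0.2/0.1317 = 1.52, power 33%.
- f = 0.2: variance 0.0258, 0.2/0.1607 = 1.24, power 24%.
- f = 0.1: variance 0.0452, 0.2/0.2126 = 0.94, power 15%.

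For 40 points against 0, the same formula gives 86%, 70% and 47%.

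**The case against.** The strongest reply is that the harm depends on enrolment, which the documents do not forecast. That stands. A reader might infer that the analysis cannot be carried out for Non-Caucasian subjects or the older age bands. The documents give no size for either. All that is certain is that three age bands from 240 subjects leave at least one with 80 or fewer, and at 72 only 5–9% of fits fail. Levels near half the sample fit with almost no separation.

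A reader might also infer that having fewer remissions than parameters means the fit must fail. It does not: at 36 subjects about 11–12 remissions are expected against 13–14 parameters, yet 41–60% of fits have a finite solution. And separation can fall on a covariate while the treatment coefficient stays finite.

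A third tempting reading is that these analyses can show nothing about a differing effect. That goes too far. Finite estimates with intervals can be compared descriptively. The subgroup section makes no claim of significance, and subgroups lie outside the testing hierarchy in SAP 8.4. What is missing is a formal test and any stated limit on interpretation.

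Finally, an interaction test would itself be weak, as the power figures show. It would give a valid comparison, but not a sensitive one.

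**Conclusion.** The point holds as an inexpensive improvement to the plan. SAP 8.1.6 includes no treatment-by-subgroup term, and its model is too large for small levels: below about 40 subjects, roughly one sixth of the sample, a fit without a finite solution is frequent, and at 24 it is close to certain. At 100 or more it is rare.

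These sizes rest on assumed covariate distributions, on 13 or 14 parameters under assumed coding, on 20–30% remission at 150 mg, and on reading the section as a fit within each level. Actual level sizes are unknown.

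A reader might take this as a flaw in the trial's findings. SAP section 11 rules that out: with three randomized subjects the analyses are not run. The correction matters for the written plan, and for any later plan that reuses the text.

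**What to change.** For each subgroup factor, fit one logistic model on the whole Full Analysis Set with treatment, the randomization stratification factors, baseline CDAI, the subgroup factor and treatment-by-subgroup. Report the interaction test. In each level, report the observed or stratification-weighted risk difference from placebo with its 95% CI, which matches the difference in proportions named as the population-level summary in SAP 8.1.1. State which of the two differences is used, and label all subgroup results exploratory.

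The change is to SAP wording only. The price is less covariate adjustment (location, duration and smoking leave the model) and an interaction test with only about 15–33% power for a 20-point versus 0-point effect, so a non-significant result must not be read as evidence of a uniform effect.

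Sparse levels do not vanish entirely. In a level of 24, with 6 placebo subjects, the chance of no placebo remission is 0.8^6 = 26%, and the interaction coefficient is then not finite. The SAP should name a fallback for that case, such as a penalized (Firth) fit. The observed risk difference can still be calculated.

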8.2 Secondary Efficacy Endpoints

8.2.1 Secondary Efficacy Analyses

If all both null hypotheses of OPS-2071 600 mg BID, 300 mg BID versus placebo in the primary endpoint of clinical remission are rejected with an experiment-wise Type I error of 0.05 by the test procedure provided in session 8.1.1, a formal test of the secondary efficacy endpoint of endoscopic response (defined as a reduction of the SES-CD by at least 50%) for comparisons of OPS-2071 600 mg BID versus placebo and 300 mg BID versus placebo will be conducted, using a similar procedure used for the primary

endpoint of clinical remission except replacing baseline CDAI with baseline SES-CD score.

The other secondary efficacy endpoints of this trial are listed below by the order of the gatekeeping test procedure:

- 2) Change from baseline in the SES-CD score.
- 3) The percentage of subjects with PRO-2 remission (defined as stool frequency ≤ 3 times per day and abdominal pain ≤ 1) at Week 12.
- 4) The percentage of subjects with clinical response, defined as at least a 25% decrease in the CDAI score, at Week 12.
- 5) The percentage of subjects who, at Week 12, achieve endoscopic remission (defined as a SES-CD score of 0 to 2; or a score of 0 to 4, with no individual subscore greater than 1).
- 6) The percentage of subjects with a decrease from baseline of ≥ 100 points in the CDAI score.

Analysis of secondary endpoint #2 will be conducted using a procedure similar to the analyses of the secondary endpoint of endoscopic response, except the logistic regression will be replaced by an analysis of covariance (ANCOVA). The model used in the analysis of the primary endpoint will be applied to secondary endpoints #3, #4, and #6, while the model used in the analysis of the secondary endpoint of endoscopic response will be applied to the analysis of secondary endpoint #5. The multiplicity handling along with the gatekeeping to protect the experiment wise Type I error in the primary and secondary analyses are detailed in section 8.4.

A sensitivity analysis of secondary endpoint #3 (PRO-2 remission) of missing data will also be provided similar to the sensitivity analysis of the primary endpoint of CDAI clinical remission. Specifically, missing data for PRO-2 remission will be imputed for the subjects who withdraw from the trial before the Week 12 visit without increasing dosages of baseline Crohn's disease medications or taking a new medication for Crohn's disease during the double-blind treatment period. The missing data under this scenario is considered as MNAR and will be imputed by applying a regression approach¹ to the abdominal pain and stool frequency scores, averaged over a 7-day period. In detail, the placebo-based pattern imputation procedure follows these steps:

- 1) Using Monte Carlo Markov Chain (MCMC) methodology from PROC MI by treatment group to impute the intermittent missing data to a monotone missing pattern;
- 2) Using pattern-mixture model approach to impute the monotone missing data. By applying MNAR statement of PROC MI in SAS, missing values under MNAR will be imputed. Only the observations in the placebo control group will be used

to impute the missing values by using the MODEL option in the MNAR statement. The imputed values for the 3 treatment groups of OPS-2071 will be adjusted using the shift parameter; When the shift parameter is 0, the MI procedure would produce an analysis which is essentially something called “back to placebo”;

- 3) The PRO-2 remission status for the subjects with the imputed data will be determined by checking if the imputed stool frequency score is ≤ 3 and the imputed abdominal pain score is ≤ 1 ;
- 4) Using logistic regression model in the primary analysis to analyze the completed data along with the imputed data;
- 5) Obtaining the overall results using PROC MIANALYZE.

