3.7.2.3 Two-item Patient Reported Outcome (PRO-2)

The PRO-2 is a symptom control measure based on 2 patient-reported components (stool frequency and abdominal pain) of the CDAI. Further details will be provided in a study manual.

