The other secondary efficacy endpoints of this trial are listed below by the order of the gatekeeping test procedure and tested after the rejection of all the null hypotheses in the primary and the first secondary efficacy endpoints. Formal test of the secondary efficacy endpoint #2 will start with a comparison of pooled OPS-2071 600 mg BID and 300 mg BID versus placebo. If it is significant, comparisons of 600 mg BID versus placebo and 300 mg BID versus placebo will be performed. If both comparisons are significant, formal comparison of OPS-2071 150 mg BID versus placebo will be conducted for the secondary efficacy endpoint #2. If this comparison is again significant, analysis of the secondary efficacy endpoint #3 will start using the same procedure, up to the secondary efficacy endpoint #6. Overall, this analytical procedure along with the gatekeeping protects the experiment-wise Type I error in the primary and secondary analyses.

- 2) Change from baseline in the SES-CD score.
- 3) The percentage of subjects with PRO-2 remission (defined as stool frequency ≤ 3 times per day and abdominal pain ≤ 1) at Week 12.
- 4) The percentage of subjects with clinical response, defined as at least a 25% decrease in the CDAI score, at Week 12.
- 5) The percentage of subjects who, at Week 12, achieve endoscopic remission (defined as a SES-CD score of 0 to 2; or a score of 0 to 4, with no individual subscore greater than 1).
- 6) The percentage of subjects with a decrease from baseline of ≥ 100 points in the CDAI score.

Analysis of secondary endpoint #2 will be conducted using a procedure similar to the analyses of the secondary endpoint of endoscopic response, except the logistic regression will be replaced by an analysis of covariance (ANCOVA). The model used in the analysis of the primary endpoint will be applied to the analysis of secondary endpoints #3, #4, and #6, while the model used in the analysis of the secondary endpoint of endoscopic response will be applied to the analysis of secondary endpoint #5.

For the PRO-2 score used to derive PRO-2 remission, the abdominal pain score is reported as the daily worst abdominal pain (0 to 3) score and the stool frequency score is recorded as the number of loose or watery bowel movements (Bristol stool form scale 6 or 7) per day; both scores are averaged over a 7-day period.

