8.1.2 Primary Efficacy Analysis

Logistic regression with terms of treatment group, the randomization stratification factors, location of disease, country, age, sex, disease duration, smoking habit, and baseline CDAI, and baseline CDAI with CDAI stratification factor interaction will be applied to the primary endpoint. The FAS will be used in the efficacy analysis.

The primary analysis of this trial is comparison of the pooled OPS-2071 600 mg BID and 300 mg BID treatment groups with placebo in the primary endpoint of clinical remission.

If this analysis is significant at a 2-sided alpha level of 0.05, comparisons to OPS-2071 600 mg BID versus placebo and OPS-2071 300 mg BID versus placebo in the primary endpoint will be conducted with a 2-sided alpha level of 0.05 in each comparison. If the comparison of the pooled OPS-2071 dose groups versus placebo in the primary endpoint is significant at a 2-sided alpha level of 0.05, and a comparison, say, OPS-2071 600 mg BID versus placebo, is also significant at a 2-sided alpha level of 0.05, the null hypothesis of equal response of OPS-2071 600 mg BID and placebo in the primary endpoint will be considered rejected with an experiment-wise Type I error of 0.05.

The comparison between OPS-2071 150 mg BID versus placebo in the primary endpoint is considered as a secondary analysis and the details are provided in section 8.4.

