8.3 Exploratory Endpoint

8.3.1 Exploratory Endpoint Analyses

The CDAI score and PRO-2 score will be evaluated at baseline and at Weeks 2, 4, 6, 8, 10, and 12 in this trial, so that the by-visit analysis of CDAI remission and PRO-2 remission (exploratory endpoints #1 and #2) at Weeks 2, 4, 6, 8, and 10, in addition to Week 12, will be provided and analyzed using a similar method with Week 12 replaced by Weeks 2, 4, 6, 8 or 10. Since the by-visit analysis of an endpoint is considered as supplemental to the analysis of the endpoint at Week 12, no adjustment in alpha is necessary.

Additional exploratory endpoints are as follows:

- 3) The percentage of subjects with a biological response in subjects with elevated levels of CRP, defined as a reduction in the level of CRP to within the normal range or by at least 15%, at Week 6, Week 12, and at the 30-day follow-up.
- 4) The percentage of subjects with a biological response in subjects with elevated levels of FCP, defined as a reduction in the level of FCP to within the normal range or by at least 15%, at Week 6, Week 12, and at the 30-day follow-up.
- 5) Characterization of the fecal microbiota profile and abundance based on taxonomic and functional annotation from next-generation sequencing, change from baseline, and association with phenotype, at Week 2, Week 12, and at the 30-day follow-up.

CMH test stratified by the randomization stratification factors will be applied to the exploratory endpoint #3 and #4. The mean change from baseline will be provided by visit for the additional exploratory endpoints#5. An analysis of covariance (ANCOVA) with baseline value as covariate and treatment as main effects will be applied to this endpoint.

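### PRO-2 remission is adjusted for baseline CDAI rather than for its own collected baseline stool frequency and pain; matching the covariates should give equal or modestly higher power

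*SAP*

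**What the plan says.** The primary model (SAP 8.1.2, Protocol 7.4.1) is "Logistic regression with terms of treatment group, the randomization stratification factors, location of disease, country, age, sex, disease duration, smoking habit, and baseline CDAI", followed by the interaction of baseline CDAI with the CDAI stratum. SAP 8.2.1 extends it: "The model used in the analysis of the primary endpoint will be applied to secondary endpoints #3, #4, and #6". Protocol 7.4.2 agrees: "The model used in the analysis of the primary endpoint will be applied to the analysis of secondary endpoints #3, #4, and #6". Exploratory endpoint #2, by-visit PRO-2 remission, follows by reference, because SAP 8.3.1 uses a similar method with the visit changed.

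For endoscopic response, SAP 8.2.1 uses the primary procedure "except replacing baseline CDAI with baseline SES-CD". That covariate carries over to #2 (change in SES-CD) and #5 (endoscopic remission).

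SAP 8.3.1 confirms that the matching PRO-2 baseline exists: "The CDAI score and PRO-2 score will be evaluated at baseline". It comes from the screening diary (Protocol 3.7.2.4). Protocol 3.7.2.3 states the link between the two scores: "The PRO-2 is a symptom control measure based on 2 patient-reported components (stool frequency and abdominal pain) of the CDAI".

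**The concern.** The plan pairs almost every secondary efficacy endpoint with the baseline of the same scale. Endpoints #1, #2 and #5 are SES-CD outcomes adjusted for baseline SES-CD, and #4 and #6 are CDAI outcomes adjusted for baseline CDAI. Only #3 lacks its own baseline, and no reason is given.

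The CDAI adds well-being, complications, antidiarrheal use, abdominal mass, hematocrit and weight to stool and pain. Two subjects with the same CDAI can therefore start at quite different distances from the remission limits of 3 stools per day and pain of 1. If baseline stool and pain predict their Week 12 values, a model that holds them only inside a composite leaves some outcome variation unexplained and gives a weaker treatment test. What is at stake is some power on one endpoint in the formal testing sequence, not the validity of the test.

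**Working it through.** **1. The plan's own figure.** No rate or power is stated for PRO-2 remission, so the primary-endpoint planning (SAP section 4) is the anchor: 40% vs 20%, 60 per arm, 2-sided alpha 0.05. The formula is power = Φ[(p1 − p0 − 1.96·SE0)/SE1], where SE0 uses the pooled proportion and SE1 the separate proportions.
- Pooled doses, 120 vs 60: p̄ = (120×0.40 + 60×0.20)/180 = 0.333; SE0 = √(0.333×0.667×(1/120 + 1/60)) = 0.0745; SE1 = √(0.24/120 + 0.16/60) = 0.0683. Power = Φ[(0.20 − 1.96×0.0745)/0.0683] = Φ(0.789) = 78.5%. The plan states 80%.
- Single dose, 60 vs 60: p̄ = 0.30; SE0 = 0.0837; SE1 = 0.0816; Φ(0.441) = 67.0%. The plan states 67%.

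Both agree to within 2 points.

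**2. How much of PRO-2 the CDAI already carries.** The CDAI weights are 2 for the weekly stool sum and 5 for the weekly pain sum (Protocol Appendix 2). Entry requires stool frequency above 3 and pain above 1 (inclusion criterion 3). At those limits the two items supply 3×7×2 + 1×7×5 = 42 + 35 = 77 points of a score between 180 and 450. They are a real part of the CDAI, but not most of it at these limits.

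**3. Number of parameters.** The swap removes two terms (baseline CDAI and its interaction with the two-level stratum) and adds two (baseline stool, baseline pain).

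**4. Power by simulation, pooled doses vs placebo.** Rates, correlations and item distributions are assumptions in every run. Below, r is the baseline-to-Week-12 correlation of each item. The remaining terms of the primary model (country, age, sex and so on) are not part of the comparison.

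Run B: 4,000 trials per scenario, 20% vs 40%, stool-pain correlation 0.3, no truncation at entry and no stratum term. The columns give the assumed correlation of CDAI with the stool-plus-pain composite; entries are power with baseline CDAI → power with baseline stool and pain.

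| r | 0.5 | 0.7 | 0.85 |
|---|---|---|---|
| 0 | 78.3 → 78.1 | 78.4 → 78.4 | 78.4 → 78.5 |
| 0.2 | 78.5 → 79.0 | 77.9 → 78.4 | 78.3 → 78.8 |
| 0.4 | 78.0 → 80.8 | 80.0 → 82.0 | 79.2 → 80.3 |
| 0.6 | 80.0 → 85.8 | 83.2 → 86.9 | 85.1 → 87.0 |

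Three further runs kept the CDAI stratum in both models. Entries are the change in power, in points:

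| Run | r = 0 | 0.2 | 0.3 | 0.5 | 0.7 |
|---|---|---|---|---|---|
| A: about 22% vs 36–38%, 2,500 trials | – | – | +0.6 | +2.6 | +8.1 |
| C: 20% vs 40%, entry limits applied, CDAI built from its weights, 3,000 trials | −0.1 | +0.9 | +0.4 | +3.2 | +5.2 |
| D: entry limits applied, 1,500 trials | +0.4 | – | +0.7 | +1.4 | +6.0 |
| D, with 20% set to failure | +0.3 | – | +0.8 | +2.5 | +4.1 |

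Simulation error on the differences in C is 0.3 to 0.5 points.

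**5. Where the gain arises.** In B at r = 0.6 and CDAI-composite correlation 0.7, the mean log odds ratio and SE are 1.132 and 0.403 with CDAI (ratio 2.81), and 1.276 and 0.433 with stool and pain (ratio 2.95). The SE rises, but the conditional log odds ratio rises more.

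**The case against.** The strongest reply is that nothing here is an error. Baseline CDAI is prespecified and valid, and it already contains related forms of both PRO-2 items. The SES-CD swap was needed in a way this one is not, because the CDAI has no endoscopic content. This stands, and it is why the loss is confined to the part of stool and pain that the composite does not carry.

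Entry truncation and the rule that counts withdrawals and medication changes as failures might be expected to remove the gain. Runs C and D applied the entry limits, and D also set 20% to failure; the gain shrinks at high correlation but remains.

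Endpoint #3 is also seldom reached. Twelve comparisons must succeed first: three on the primary endpoint, three on endoscopic response (if the pooled gate is repeated there), two for 150 mg, and four on #2. At the planning rates, with 150 mg assumed as effective as the higher doses, all primary steps succeed about 45% of the time and all endoscopic steps about 41%. The chance of passing both is at most 41%, or about 0.45×0.41 = 18% if the endpoints are independent, before #2 is tested. If 150 mg has half the effect, these fall to at most 19% and about 4%. This stands: a stand-alone power gain overstates the effect on formal success.

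A reader might infer that the plan discards precision that could be had free. The documents do not support that. The SE of the log odds ratio does not fall. The 8.1-point figure in run A needs a correlation of 0.7, and no correlation is stated anywhere. Nor is the change cost-free: SAP 8.2.2 has a scaling fault in the PRO-2 derivation, and the Full Analysis Set guarantees a baseline CDAI but not a baseline PRO-2.

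**Conclusion.** The point holds as a modest improvement. Endpoint #3 and exploratory #2 are the PRO-2 analyses left without a matched baseline, although that baseline is collected. Replacing the CDAI terms should leave power unchanged or raise it: about 0 to 1 point for r of 0.3 or below, and roughly 1 to 6 points for r of 0.4 to 0.7. The 8.1 points in run A lie above the 4.1 to 6.0 found at the same correlation with the entry limits applied, and should not be used as the expected gain. All sizes rest on assumed PRO-2 rates (mostly borrowed from the primary endpoint) and assumed correlations. Only the direction, and the absence of a visible power cost at r = 0, are consistent across the runs. Type I error is not affected. Practical weight is low, given the testing order and SAP section 11, which records that only three subjects were randomized and that the analyses will not be carried out. The value is in any reuse of the plan.

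**What to change.** For secondary endpoint #3 and exploratory endpoint #2, replace baseline CDAI and its stratum interaction with baseline 7-day mean stool frequency and baseline 7-day mean abdominal pain. Keep the CDAI stratum as a factor. Make the same change in Protocol 7.4.2, in the model sentence of SAP 8.2.1, in step 4 of the PRO-2 sensitivity analysis in that section (which reuses the primary logistic model), and in SAP 8.3.1.

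Two things must be settled with it:
- SAP 8.2.2 item 2 defines PRO-2 scores as daily averages but, with 1 or 2 days missing, multiplies the 6- or 5-day average by 7. Taken literally, a subject averaging 5 stools per day would enter as 35. Delete the multiplication for PRO-2; it belongs to the CDAI weekly sums.
- State how a missing baseline PRO-2 item is handled so that no subject in the Full Analysis Set drops out of the model, for example by simple imputation of the baseline value.

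The cost is a few aligned sentences, with no extra data and no net increase in model terms.
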